4.1 Efficacy Evaluation (if applicable)

N/A

4.2 Pharmacokinetic Evaluation (if applicable)

N/A

4.3 Safety Evaluations

N/A

STATISTICAL CONSIDERATIONS

4.4 Statistical Methods

Primary Aim:

Our primary analyses will test the hypothesis under the intent-to-treat (ITT) principle using Generalized Linear Mixed Models (GLMM) that account for the clustering of child care centers within regions/TA. The primary GLMM will include a random intercept for region (b_0) and fixed effects for the baseline value of the primary outcome (β_1) and the intervention (β_2) to test if the differences in mean changes in primary outcomes is zero, where β_0 is the fixed intercept, and e is error.

$$\text{Change in Primary Outcome}_{12m} = \beta_0 + \beta_1 \text{ Primary Outcome}_{\text{baseline}} + \beta_2 \text{ Intervention} + b_0 + e$$

To further explore the intervention effect, we will examine: 1) baseline covariates relevant to change in EPAO scores; 2) interaction between treatment group and other covariates; and 3) completers only. Baseline demographics and EPAO scores will be compared between centers with and without follow-up measures to inspect for potential bias.

Secondary Aims:

Analysis for secondary aims will use statistical models like those applied for primary analysis. Generalized Linear Mixed Models (GLMM) that account for the clustering of child care centers within regions/TA under the intent to treat principle will be utilized. The primary GLMM will include a random intercept for region and fixed effects for the baseline value of the outcome and the intervention. Interaction terms will be added to models where needed. Specifics relevant to aims 2-5 include:

Aim 2. Data used to evaluate adoption, implementation, and maintenance of Basic vs. Enhanced Go NAPSACC will be compiled from the Go NAPSACC registration reports and activity reports (Center and TA). Outcomes computed from these reports include: registration, account initiation, first self-assessments, selection of goal, creating action plans, post cycle self-assessment, TA contacts, and TA implementation activities.

Aim 3. Section 1.4 includes a summary of the organizational factors outcomes that will be assessed. In short Fernandez's CFIR Inner Setting: Culture, Culture Stress, Culture Effort, Implementation Climate, Leadership Engagement, and Available Resources along with TCU's Organizational Readiness for Change: Networks and Communications and Access to Knowledge and Information will be collected from surveys completed by directors, teachers, and TA coaches. Organizational outcomes will be examined as moderators of the intervention effects in statistical models. Both continuous and categorical (quartiles) moderation effects will be tested.

Aim 4. Details about computing program cost can be found in section 1.4. The average incremental cost of delivering Enhanced Go NAPSACC will be divided by the incremental change in effectiveness (relative to Basic Go NAPSACC) to quantify the incremental cost-effectiveness ratio. The Incremental Cost-Effectiveness Ratio includes costs over the time period of the study and effectiveness measured by the unit increase in EPAO score. Standard GLMM models will be used to compare cost ratios between intervention groups.

Aim 5. Diet and activity information from the EPAO-sr (see section 1.4) will be used to diet quality of the food served to children and the physical activity time provided. Food and meal reporting will be used to summarize center-level dietary intake and to calculate diet quality (Healthy Eating Index 2015), while daily activities reporting will be used to summarize the activity levels of children. Outdoor time, active indoor time, vigorous minutes, and teacher ratings of activity level will be used to calculate an activity level index. Analysis and statistical models used to evaluate this aim will be nearly identical to those for primary analysis.

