Number Of Subjects	
TA Coaches: BL n = 27; FU n = 26
 
Child Care Centers: BL n = 97; FU n = 88
 
Child Care Providers: BL n = 257; FU old n = 139, FU new n = 82

Study Duration	Each subject's participation will last approximately 14 months; 1 month for baseline data collection, 12 months of intervention, and 1 month of follow up data collection. The entire study is expected to last approximately 3 ½ years.
Study Phases	
(1) Screening and recruitment: During this phase we will identify and recruit TA coaches and get lists of the centers they serve. Centers will be screened for eligibility and recruited randomly. After a director and teachers consent, baseline data collection will be completed (2) Intervention: After baseline measurement, TAs will be randomly assigned to Basic or Enhanced Go NAPSACC implementation and the 12-month intervention will proceed (3) Follow-Up: After the 12-month intervention, follow up measures and process evaluations will be completed.

Efficacy Evaluations	
 • Primary Objective 
 ○ Aim 1. Compare intervention impact on implementation of healthy weight practices. 
 ▪ EPAO-SR Nutrition and Physical activity environment scores. • Secondary Objectives 
 ○ Aim 2. Evaluate adoption, implementation, and maintenance by group. 
 ▪ Percent of centers creating accounts, completing self-assessments, selecting goals, and creation of action plans will be captured by the Go NAPSACC website and extracted using the registration and detailed activity reports. ○ Aim 3. Examine how organizational factors predict implementation. 
 ▪ Surveys completed by directors, teachers, and TA coaches. ▪ Fernandez's CFIR Inner Setting: Culture, Culture Stress, Culture Effort, Implementation Climate, Leadership Engagement, and Available Resources. ▪ TCU's Organizational Readiness for Change: Networks and Communications and Access to Knowledge and Information. ○ Aim 4. Calculate incremental cost-effectiveness ratio for environment change. 
 ▪ Costs include TA coaches time and any resources required to train and support centers for 12 months. Costs will be tracked in the TA Activity and

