2.1 Study Design

This study will use a two-arm cluster randomized controlled design. The unit of randomization is the TA coach, and child care centers will be subject to the same randomization assignment as their TA coach.

In order to be randomized, TA coaches must complete baseline measures and their associated centers must have all participants recruited and baseline data collection must be complete. Once randomized to either Basic Go NAPSACC or Enhanced Go NAPSACC, TAs and centers will be involved in intervention for 12 months. Then follow-up data will be collected from TAs and centers.

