2.3 Study Duration, Enrollment and Number of Subjects

Study duration varies by participant type. TA coaches will be involved for approximately 18 months, center directors for approximately 16 months, and teachers for approximately 4 weeks.

The goal is to enroll 97 centers, a director and at least 1 teacher at each center. When possible, we will recruit 2 teachers who work with children 3-5 years old at each center. We will enroll 8 TA coaches across the 8 regions of Kentucky through Child Care Aware of Kentucky (Northern Bluegrass, Southern Bluegrass, Salt River Trail, Eastern Mountain, Cumberland, Two Rivers, Jefferson, and The Lakes). This will be done across 4 waves.

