9. RECRUITMENT STRATEGY

The 97 centers will be recruited over 4 waves from the 11 regions that span the state. We will work with Child Care Aware Kentucky and identify Technical Assistants in each region. We will then identify all licensed child care centers that each TA works with and randomly select a sample of 25 centers for each TA to target for recruitment. TA providers will help distribute recruitment materials (provided by the project) to the child care centers and gauge initial their interest. The names and contact information from interested centers will be supplied to the project team for follow-up. Trained research assistants will follow up with interested centers by telephone to review study details, confirm eligibility, and verify interest of the center. Once participation is confirmed, two 3-5 year old classroom teachers will be chosen to be recruited. A follow up email with information to go over with potential teachers. Then those teachers would be called at the center and recruited by phone to review study materials and confirm interest.

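### The primary model's only random intercept is for region, but TA coaches were randomized and 27 coaches sit in 8 to 11 regions, so the standard error omits the clustering that randomization created

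*Combined protocol and SAP*

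**What the plan says.** - **Randomized unit.** Section 2.1: "The unit of randomization is the TA coach, and child care centers will be subject to the same randomization assignment as their TA coach". Section 3.1 repeats that each coach delivers the assigned model to all of that coach's enrolled centers.
- **Primary model.** Section 4.4 says the models "account for the clustering of child care centers within regions/TA". The specification that follows has one random effect: "The primary GLMM will include a random intercept for region (b_0". The equation contains a fixed intercept, the baseline value, the intervention, b_0 and error. The synopsis gives the same model, and the secondary-aim text in section 4.4 repeats the region intercept.
- **Number of coaches.** Section 2.3: "We will enroll 8 TA coaches across the 8 regions of Kentucky". The synopsis (Number Of Subjects): "TA Coaches: BL n = 27; FU n = 26".
- **Number of regions.** Eight in section 2.3. Section 9 says centers are "recruited over 4 waves from the 11 regions that span the state".
- **Number of centers.** Synopsis: "Child Care Centers: BL n = 97; FU n = 88".
- **ICC.** Section 4.5 uses 0.001, taken from a pilot of 31 centers in 3 regions and describing centers in the same region. No coach-level ICC and no degrees-of-freedom method are given.

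**The concern.** In a cluster-randomized trial the error term for the treatment contrast has to contain the variation between randomized units. Here the unit is the coach, who also delivers the intervention: coaches run the orientation and check-ins in both arms and, in Enhanced, feed back the readiness results and host the cross-center meetings. Centers that share a coach may well change together for that reason alone.

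If several coaches work in one region and fall in different arms, a region intercept cannot represent that shared change. Most of it goes into the residual, which the model takes as independent from center to center. The standard error for Enhanced versus Basic is then too small, the interval too narrow and the type I error above nominal, by an amount that grows with the coach ICC. The degrees of freedom should also reflect about 26 coaches, not 88 centers. The primary comparison is affected, and so are the secondary models that reuse the structure.

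**Working it through.** **1. Can region equal coach?** 27/11 = 2.5 and 27/8 = 3.4 coaches per region on average. With 27 coaches, at least one region must hold three or more coaches if there are 11 regions, and four or more if there are 8. The two levels cannot be the same.

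**2. The plan's own sample size.** Total N = 4 × ((z₀.₉₇₅ + z₀.₈₀)/d)² × [1 + (m − 1) × ICC], two-sided, 1:1, with d = 0.6 and ICC = 0.001.
- 4 × (2.802/0.6)² = 87.2
- m = 10: 87.2 × 1.009 = 88.0
- m = 15: 87.2 × 1.014 = 88.4

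Both match the table in section 4.5, so that arithmetic is not in question. Its cluster is the region, with 10–15 centers.

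**3. The same formula at coach level.** Centers per coach: 97/27 = 3.6 at baseline and 88/26 = 3.38 at follow-up. The design effect is 1 + 2.38 × ICC. Power is for 88 centers and d = 0.6, with a t test on 26 − 2 = 24 df.

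| Coach ICC (assumed) | Design effect | N for 80% power (normal approx.) | Power at 88 centers |
|---|---|---|---|
| 0.001 | 1.002 | 87 | 77% |
| 0.01 | 1.024 | 89 | 76% |
| 0.05 | 1.119 | 98 | 72% |
| 0.10 | 1.238 | 108 | 68% |
| 0.20 | 1.477 | 129 | 60% |

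**4. Type I error of the model as written.** Data were simulated with no treatment effect and no region effect: 26 coaches, 88 centers, unequal caseloads, 8 or 11 regions, and coaches spread evenly over regions, with and without balancing arms within region. There were 2,500 trials per setting (Monte Carlo standard error √(0.05 × 0.95/2500) = 0.004). Each data set was fitted by REML with a region intercept (z test) and with a coach intercept (t, 24 df). Ranges run over the four layouts.

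| Coach ICC | Region intercept (as written) | Coach intercept, 24 df |
|---|---|---|
| 0 | 0.048–0.057 | 0.032–0.038 |
| 0.01 | 0.056–0.065 | 0.034–0.041 |
| 0.05 | 0.067–0.074 | 0.039–0.048 |
| 0.10 | 0.079–0.100 | 0.041–0.052 |
| 0.20 | 0.122–0.132 | 0.045–0.051 |

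A larger run with 18,000 data sets per setting agrees: 5.2% at ICC 0.001, about 6% at 0.02, 7% at 0.05, 9% at 0.10 and 12–13% at 0.20 for the region model, against 3.5–5.1% for the coach model.

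**5. Size of the standard-error shortfall.** Mean model standard error against the empirical SD of the estimate, region-intercept model:
- ICC 0.01: about 4% too small or less
- ICC 0.10, 8 regions: 0.214–0.220 against 0.251–0.258, about 15% too small
- ICC 0.20, 8 or 11 regions: 0.210–0.224 against 0.272–0.284, 21–23% too small

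The region intercept therefore absorbs only a little of the coach variance.

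**The case against.** **The label may simply be out of date.** The plan treats region and coach as one unit: 8 coaches in 8 regions, regional TA providers, and 10–15 centers per region beside 12–13 per provider. In that design the region intercept is the coach intercept and the model is right. The text also names TA clustering as something it means to cover. This explains how the mismatch arose and shows the intent. It does not supply a coach term: b_0 is explicitly region, and an analyst who follows the equation leaves out the randomized level.

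**The layout is not documented.** The 27 is a baseline count, and section 2.1 makes randomization conditional on completed baseline data. Coaches per region and arms by region are not reported. That is correct, and the simulated layouts are assumptions. But 26 coaches were still counted at follow-up, far above 8, and no region-level assignment is described.

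**The only ICC in the plan is 0.001.** At that value there is no practical inflation, and the larger figures need coach ICCs that the documents do not support. This limits what can be claimed about size. However, 0.001 is a region correlation from three regions. Where coaches are regional it is not wholly uninformative, but it cannot rule out a larger coach ICC under coach-delivered support.

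**No test statistic is named.** The z test in the simulation is therefore a supposition. What stands is that the degrees-of-freedom method is unspecified.

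**Conclusion.** The concern holds. The written primary model does not represent the randomized unit, and with 27 coaches in 8 or 11 regions the region intercept cannot stand in for it. The error is anti-conservative. At nominal 5%, the type I error is about 6% for coach ICCs of 0.01–0.02, about 7% at 0.05, 8–10% at 0.10 and 12–13% at 0.20, with no visible inflation at 0.001.

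These figures assume 26 analyzed coaches, 88 centers, coaches spread evenly over regions, arms that cross regions, and no region effect. The coach ICC range is assumed. The size of the distortion is therefore uncertain, but the mismatch between model and randomization is not. As written, the primary test is valid only if coach-level correlation is close to zero, and nothing in the plan establishes that. This should be corrected before the analysis is run.

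**What to change.** - In section 4.4 and the synopsis, define b_0 as a random intercept for TA coach, the randomized unit. Region may be kept as an additional term.
- State the test for β₂ with small-sample degrees of freedom: Kenward–Roger, or the number of coaches minus 2.
- Make the same change to the models for Aims 2–5.
- Reconcile the coach counts (8 and 27) and the region counts (8 and 11). State how many coaches were randomized to each arm and how they fall across regions.

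**Cost.** A line of SAP wording and of model code, and no new data, because coach identity defines the assignment. If the true coach ICC is zero, the interval is somewhat wider. In the simulation the mean standard error is 0.224–0.226 against 0.215–0.218, and the multiplier is 2.064 (24 df) instead of 1.960, so the interval is about 8–11% wider. The lower power in the coach-level table comes from the randomized design; the region-intercept model only conceals it.

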Test Article(s) (If Applicable)	
TA Coaches are randomized to provide Basic Go NAPSACC or Enhanced Go NAPSACC delivery to their enrolled centers.
 
In Basic Go NAPSACC (general prescription) TA Coaches will:
 
• invite their centers to register, complete self-assessments, and create action plans• encourage centers to complete 2 cycles of Go NAPSACC’s 5-step improvement process• check in monthly to evaluate progress, provide suggestions, and trouble shoot issues. 
In Enhanced Go NAPSACC TA Coaches will:
 
• Help center create an implementation team, conduct a readiness assessment, and guide choice of a priority challenge for each center.• Invite centers to register and complete self-assessments.• Help director create an implementation plan for the improvement process. This plan will be tailored based on the priority challenge identified from readiness assessment.• Check in monthly to evaluate progress, provide suggestions, and trouble shoot issues.• Facilitate quarterly cross-center meetings to create community and discuss issues.• Participate in a group check-in with a Go NAPSACC advisor (UNC research team) monthly and talk with UNC team individually each quarter.

Study Design	This is a type 3 hybrid effectiveness-implementation RCT with a clustered parallel group intervention design. TA coaches were randomized to deliver Basic Go NAPSACC or Enhanced Go NAPSACC to their enrolled centers.
Subject Population Key criteria for Inclusion and Exclusion:	
For this study we will recruit Technical Assistants (TA Coaches) and child care centers. From each center, we will recruit and enroll a director and 2 teachers.
 
TA Coaches
 
 • Must either be Quality coach or a Healthy and Safety coach • Must be able to read and speak English 
Child Care Centers
 
 • Must be part of a participating TA coach's current caseload • Have no plans to close in the coming year • Have at least one classroom serving preschool children • Serve at least lunch to the children • Not serve special needs children exclusively 
Child Care Providers
 
 • Teacher must be the lead teacher in a preschool classroom • Center directors and teachers must be able to read and speak English

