1.2 Secondary Objective

- Aim 2. Evaluate adoption, implementation, and maintenance of Basic vs. Enhanced Go NAPSACC.
 - *Hypothesis 2.* Reach, adoption, implementation, and maintenance (as defined by RE-AIM) will be higher among centers receiving Enhanced Go NAPSACC compared to centers receiving Basic Go NAPSACC.
- Aim 3. Examine how organizational factors predict implementation under Basic vs. Enhanced conditions.
 - *Hypothesis 3.* Positive organizational factors (as defined by CFIR), such as communication, culture, implementation climate, and readiness, will enhance implementation of Go NAPSACC.
- Aim 4. Calculate incremental cost-effectiveness ratio of Basic vs. Enhanced Go NAPSACC in terms of changing centers' environments.
 - *Hypothesis 4.* Both Enhanced and Basic Go NAPSACC will be cost-effective in terms of costs per outcome achieved, but Enhanced Go NAPSACC will be more efficient than Basic Go NAPSACC.
- Aim 5. Compare Basic vs. Enhanced Go NAPSACC's impact on children's diet quality and physical activity at child care.
 - *Hypothesis 5.* Children enrolled at centers receiving Enhanced Go NAPSACC will have higher diet quality and spend more time in physical activity while at child care compared to children at centers receiving Basic Go NAPSACC.

2 INVESTIGATIONAL PLAN (brief overview)

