For centers receiving Enhanced Go NAPSACC, the director will work with their TA coach to identify an implementation team to support the use of the program and improvements in nutrition and physical activity practices. The team will include a center administrator as well as two staff (at a minimum). Before starting Go NAPSACC, the team will work with their TA coach to conduct an assessment of their center's needs, capacity, and resources. At a minimum this readiness check will be completed by all members of the team, but the team can also extend participation out to all center staff. The readiness check will be completed anonymously and returned to the TA coach for scoring. Summarized results will be presented back to the team by the TA coach and used to identify priority issues for which the team would like extra support from the TA coach as they are working through Go NAPSACC.

Once this readiness check is complete, the team will begin their use of Go NAPSACC. All members of the team will be invited to register for a Go NAPSACC account, linked back to their child care center. The team will then participate in a 1-hour orientation provided by their TA coach to learn how to use Go NAPSACC's online tools and resources. Once the team is trained, they will be encouraged to complete 2 cycles of Go NAPSACC's 5-step improvement process focusing on child nutrition and physical activity. The team will be asked to develop a 12-month plan to guide their Go NAPSACC efforts. In each cycle of Go NAPSACC, the team will:

- Evaluate their current nutrition and physical activity practices using the self-assessments in these two modules.
- Choose at least 3 goals per module and create an action plan for each goal using online tools that offer flexible step-by-step guidance.
- Work to implement the action plan and meet their chosen goals drawing from the tip and materials resource library.
- Log progress and completion of goals.

Each cycle will take about 5-6 months. At the end of the 12 months, the team will retake the self-assessments on child nutrition and physical activity. Throughout this process, the team will receive brief check-ins from their TA coaches via phone, email, or in-person. These check-ins will include tailored

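### Aim 2 compares raw counts of coach activities (and possibly coach contacts) between arms, although the protocol prescribes extra coach activities only in Enhanced

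*Combined protocol and SAP*

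**What the plan says.** On the source of the data for this aim, section 4.4 states: "Data used to evaluate adoption, implementation, and maintenance of Basic vs. Enhanced Go NAPSACC will be compiled from the Go NAPSACC registration reports". Center and coach activity reports are the other source. Eight outcomes follow. Six are center steps: registration, account initiation, first self-assessments, goal selection, action plans and post-cycle self-assessment. The other two are "TA contacts, and TA implementation activities".

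On analysis, section 4.4 states: "Analysis for secondary aims will use statistical models like those applied for primary analysis". That means a mixed model with an intervention effect. Hypothesis 2 in section 1.2 gives the direction: "Reach, adoption, implementation, and maintenance (as defined by RE-AIM) will be higher among centers receiving Enhanced Go NAPSACC".

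On delivery, the synopsis (Test Articles) asks coaches in both arms to "check in monthly to evaluate progress, provide suggestions, and trouble shoot issues". Section 3.2 gives both arms a one-hour orientation led by the coach. For Enhanced alone, section 3.2 adds work before the program starts, for example "the team will work with their TA coach to conduct an assessment", and later cross-center meetings hosted by the coach.

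The synopsis (Efficacy Evaluations) describes the Aim 2 measures as "Percent of centers creating accounts, completing self-assessments, selecting goals, and creation of action plans". Coach contacts and coach activities are not in that list.

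**The concern.** A count of coach activities is in part a count of what the coach was told to do. Enhanced coaches are told to do more kinds of things. A between-arm comparison of raw counts can therefore favor Enhanced when every coach simply follows the assignment and no center behaves differently.

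Under Hypothesis 2 such a difference would be read as better implementation. Section 4.4 does not label the two items as dose or fidelity, and it does not score them against each arm's own prescription. Coach time and direct contacts are also the cost input for Aim 4 (section 1.4, Cost-effectiveness). The same extra effort would count as success in Aim 2 and as cost in Aim 4.

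**Working it through.** The plan gives no target difference or power figure for Aim 2, so there is no stated number to reproduce. The check sets the coach duties side by side.

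| Center-facing coach task | Basic | Enhanced | Source |
|---|---|---|---|
| Monthly check-ins over 12 months | about 12 | about 12 | Synopsis |
| Orientation | 1 | 1 | Section 3.2 |
| Help to form an implementation team | none | yes | Synopsis; section 3.2 |
| Readiness assessment | none | yes | Synopsis; section 3.2 |
| Feedback of readiness results | none | yes | Section 3.2 |
| Help with an implementation plan | none | yes | Synopsis (section 3.2 asks the team to develop a plan and does not mention coach help) |
| Cross-center meetings | none | quarterly, or 2-3 | Synopsis; section 3.2 and the intervention description |

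**Equally prescribed part.** 12 + 1 = 13 per center in each arm. The difference is 0.

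**Contacts.** The term is not defined. If it means check-ins only, the prescription is 12 against 12 and nothing is built in. If it includes Enhanced-only sessions, Enhanced is higher by prescription.

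**Activities.** The coach log is meant to hold implementation activities, and five kinds of these are assigned to Enhanced alone. For illustration only, assume each of the four Enhanced-only tasks is logged once per center and each meeting counts once for each center:
- Basic: 13.
- Enhanced with 2 meetings: 13 + 4 + 2 = 19.
- Enhanced with 3 meetings: 13 + 4 + 3 = 20.
- Enhanced with 4 meetings (quarterly): 13 + 4 + 4 = 21.

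The counting rule is an assumption. The documents do not say how a group meeting is attributed to a center or how a task becomes a logged entry. Only the sign of the gap follows from the text.

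**Scoring against each arm's own prescription.** Full delivery gives 13/13 = 100% in Basic and 100% in Enhanced, so the built-in gap disappears. This needs a fixed denominator. Under the same counting rule, 19 delivered items would be 19/19 = 100%, 19/20 = 95% or 19/21 = 90%, depending on which meeting frequency applies.

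**Share of Aim 2 affected.** Two of eight listed outcomes, one with certainty (activities) and one conditionally (contacts).

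**The case against.** The strongest reply is that this is a type 3 hybrid trial. Coaches are the randomized unit and are themselves participants. Enhanced coaches also receive more support: monthly calls with a specialist and one-on-one sessions. Whether better-supported coaches deliver more is a real implementation question. This stands for components prescribed equally, such as check-ins, and for delivery measured against assignment. It does not rescue a raw count that includes tasks assigned to one arm only.

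It is also fair to say that no composite mixes coach and center measures. If centers did no more, the six center steps could show it. Actual delivery can also depart from the prescription, so a higher count in Enhanced is favored but not guaranteed.

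A reader might infer three stronger points that the documents do not support:
- **Account counts are inflated because Enhanced invites a whole team.** Section 3.2 does say "All members of the team will be invited to register for a Go NAPSACC account", but those accounts are linked to the center, and the synopsis gives the unit as the percentage of centers.
- **Enhanced coaches are told to log more completely.** The log instructions differ by a word or two between arms, but section 1.4 asks for planning time and every direct contact under both approaches.
- **The synopsis contradicts section 4.4.** A shorter list is not a contradiction, and the synopsis names the activity reports as a source.

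Finally, the synopsis already gives follow-up counts (88 centers), so removing outcomes now could look post hoc. That affects how the change is documented, not whether it is needed.

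**Conclusion.** The point holds in a limited form. Raw counts of coach activities, and of coach contacts if these include Enhanced-only sessions, are not clean evidence for Hypothesis 2, because part of any excess in Enhanced is assigned. The built-in gap is certain in direction for activities and depends on the definition for contacts.

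Its size cannot be fixed from the documents. The counting rule is not stated, the meeting frequency is inconsistent, and no variability is given for Aim 2 outcomes. No percentage excess or chance of a significant result should therefore be quoted.

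A reader might conclude that Aim 2 is decided in advance. It is not: six of the eight outcomes are center steps, and the primary analysis of EPAO-SR scores is untouched. The conclusion rests on two readings of the text: that the log captures the Enhanced-only tasks, and that the two items are tested between arms like the other secondary outcomes.

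**What to change.** Change the Aim 2 text in section 4.4 as follows:
- Define coach contacts and coach activities. State how group meetings are attributed to centers and whether calls between coaches and the research team are counted.
- Do not use raw counts of these two items as evidence for Hypothesis 2. Report them by arm as intervention delivered, as a proportion of what that arm prescribes.
- Compare between arms only the components prescribed equally: monthly check-ins and orientation.
- Base the Hypothesis 2 tests on the center-side steps, with the center as the unit, as in the synopsis.
- Reconcile the cross-center meeting frequency (quarterly in the synopsis, 2-3 in the intervention description and section 3.2) before the Enhanced prescription serves as a denominator.

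Record this as a dated change with its reason. Still show the raw counts descriptively, so that nothing planned is withheld. No new data are needed. The cost is SAP wording and two fewer tested outcomes for Hypothesis 2.
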